7.3.2.1. Investigation for Idelalisib Late Onset or Severe Diarrhea/Colitis

See CTCAE Version 4.03 for definitions of colitis and diarrhea.

Among idelalisib-treated patients who reported diarrhea or colitis, the median time to onset of any grade diarrhea or colitis was 1.9 months (range, 0.0–29.8), of grade 1 or 2 was 1.5 months (range, 0.0–15.2) and of grade 3 or 4 was 7.1 months (range, 0.5–29.8). Kaplan–Meier curves of time to onset of diarrhea or colitis are shown for all idelalisib- treated patients in [Figure 7-1](#) {[Coutre et al 2015](#)}.

Figure 7-1. Kaplan-Meier Time to Diarrhea or Colitis

Idelalisib-associated severe diarrhea responds poorly to antimotility agents however, median time to resolution ranged between 1 week and 1 month across trials following interruption of idelalisib treatment and, in some instances, initiation of corticosteroid treatment {[Gilead Sciences Inc 2014](#)}.

7.3.3. Hepatic Events

Transaminase Elevations: Consistent with observations in a dog toxicology study, reversible asymptomatic ALT/AST increases were also observed early in the idelalisib program in phase 1 studies (101-02 and 101-07) in subjects with hematologic malignancies. Transaminase elevations generally occurred within 4 to 12 weeks of drug initiation, and resolved spontaneously over a period of 2 to 4 weeks with drug being continued for Grade 1 and 2 elevations and drug withheld for Grade 3 or 4 elevations until resolution. These early observations have been consistent with the ongoing experience with idelalisib treatment and transaminase elevations are now well characterized as most frequently asymptomatic, transient and occurring within the first 3 months of treatment.

Grade 1 or 2 elevations commonly resolve despite continued idelalisib treatment and Grade 3 or 4 elevations can be managed by withholding idelalisib. Successful rechallenge after resolution at either the same or lower dose level of idelalisib has been achieved in the majority of subjects. There has been no evidence of impaired synthetic function. Close monitoring of hepatic laboratory tests during therapy is important to allow for appropriate idelalisib interruption and reinstitution so that subjects may continue with study drug treatment.

7.3.4. Hematological and Immunological Events

In the Phase 1 experience with idelalisib in patients with NHL and CLL, subjects with Grade ≥ 3 neutropenia, anemia, and/or thrombocytopenia were enrolled to clinical trials. Decreased levels of neutrophil counts, hemoglobin, or platelet counts during idelalisib administration were largely due to minor fluctuations in these parameters among subjects with pre-existing hematological abnormalities due to disease or prior therapy. Thus, idelalisib did not appear to induce overt myelosuppression. Obvious patterns of drug-mediated reductions in circulating CD4+ lymphocyte counts or suppression of serum IgG levels were also not observed.

Treatment-emergent Grade 3 or 4 neutropenia events, including febrile neutropenia, have occurred in subjects treated with idelalisib. All subjects should have their blood counts monitored at least every 2 weeks for the first 6 months of idelalisib treatment. For subjects who develop Grade 3 neutropenia, blood counts must be monitored at least weekly. For subjects who develop Grade 4 neutropenia, idelalisib must be interrupted and blood counts monitored at least weekly until ANC is ≥ 0.5 Gi/L, at which point, idelalisib may be resumed at a lower dose level. Neutropenia should be managed according to established clinical guidelines.

No modification of any drug for changes in circulating CD4+ counts or Ig levels is planned.

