1.4. Benefit/Risk Assessment for the Study

Subjects enrolled in this study have a serious life-threatening disease, with limited treatment options. Without treatment their disease will progress and ultimately be fatal. Transitioning subjects from GS-9820 to idelalisib, a similar agent in class that has shown proof of clinical activity and has received regulatory approval for the treatment of relapsed CLL and iNHL {[Gilead Sciences Limited 2015](#)}, is rational as described in Section 1.3 of this protocol; therefore, subjects enrolled in this study may derive clinical benefit defined as an improvement in disease control such as response to study treatment. The risks that may accompany study treatment are related to the identified and potential toxicities of treatment with idelalisib and are described in Section 5 of this protocol and in the ICF. The management of these toxicities is described in [Table 5-2](#). Taken together, there is a positive benefit/risk for initiating study treatment with idelalisib in subjects previously treated with GS-9820.

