5.2.10. Idelalisib Dose Adjustments

The dose adjustment recommendations and requirements in [Table 5-2](#) are based on the Common Terminology Criteria for Adverse Events (CTCAE) grade of specific toxicities. However, exceptions are expected for subjects who initiate study treatment with low blood counts. Clinical judgment should apply, and in cases of uncertainty, the study medical monitor should be contacted.

The dose modification instructions in [Table 5-2](#) focus on the types of events most commonly associated with idelalisib. The modifications include both recommended and required actions. When a modification is indicated as a recommendation, it serves as a guideline; variations from the recommendation may be warranted based on an investigator's individual judgment in considering potential risks, benefits, and therapeutic alternatives available to each subject.

Table 5-2. Dose Adjustment Guidelines {Gilead Sciences Inc 2014}

NCI CTCAE Grade ^a	Idelalisib
HEMATOLOGICAL ADVERSE EVENTS	
Neutropenia	
Grade \leq 2 neutropenia	Recommended Action: Maintain current dose level and schedule.
Grade \leq 3 neutropenia	Required Action: Monitor blood counts at least weekly until ANC \leq Grade 2. Recommended Action: Maintain current dose level and schedule.
Grade 4 neutropenia (or occurrence of neutropenic fever or infection)	Required Action: 
Withhold idelalisib.Monitor blood counts at least weekly until ANC \leq Grade 2 Recommended Action: 
May resume idelalisib at lower dose level when ANC grade is \leq Grade 3Neutropenia should be managed according to established clinical guidelines.
Thrombocytopenia	
Grade \leq 3	Recommended Action: Maintain current dose level and schedule.
Grade 4	Required Action: Withhold idelalisib for bruising or bleeding until Grade \leq 3. Recommended Action: May resume idelalisib at initial or reduced dose level at investigator discretion.
NON-HEMATOLOGICAL ADVERSE EVENT	
Rash	
Grade \leq 1	Recommended Action: Maintain current dose level and schedule
Grade 2	Recommended Action: Maintain current dose level and schedule
Grade \geq 3	Required Action: Withhold idelalisib until Grade \leq 1. Recommended Action: Resume at lower dose level or discontinue idelalisib at investigator discretion.
Stevens-Johnson Syndrome (SJS)/Toxic Epidermal Necrolysis (TEN)	

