6.2.2. Laboratory Assessments

Blood samples for ALT, AST, total bilirubin will be collected at Screening, Day 1, Weeks 4, 8, 12, 16, 168, every 12 weeks thereafter, and the End of Study (EOS) Visit.

Blood samples for CMV will be collected at Screening and every 4 weeks thereafter throughout study participation.

Blood samples for ANC will be collected at Screening and every 2 weeks through Week 24.

Blood samples for Pneumococcal, Haemophilus Influenzae Type B (Hib), and Tetanus titers will be taken at screening

Blood samples for immune-monitoring will be collected at Screening, Weeks 4, 12 and every 12 weeks thereafter, and the EOS Visit:

- Lymphocyte subset panel using flow cytometry (immunophenotyping)
- Quantitative immunoglobulins: IgG, IgM, IgA
- Serum CH50 level

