6.3. End of Study

Subjects will be withdrawn from this study if they develop progressive disease, unacceptable toxicity related to idelalisib, withdraw consent, are noncompliant, or are lost to follow up or die. In this event, the following procedures should be performed:

- Return of used and unused drug supply
- Recording of all Grade AEs and all SAEs
- Investigator Response Assessment
- Laboratory assessments as outlined in [Table 6-1](#)
- Recording of the reason for withdrawal
- Deaths occurring within 30 days following the last dose of idelalisib, even if occurring after the End of Study Visit, will be captured.

Table 6-1. Schedule of Study Procedures

Period	Screen	Treatment														End of study	
Visit	1	2	3	4	5	6	7	8	9	10	11	12	13	14	15+		End of study
Week	-4	0	2	4	6	8	10	12	14	16	18	20	22	24	Q4 weeks	Q12 weeks	End of study
Study Day	Within -28 days	1	14	28	42	52	70	84	98	112	126	140	154	168			End of study
Visit Window			±2	±2	±2	±2	±2	±2	±2	±2	±2	±2	±2	±2	±7	±7	
Informed consent	X																
Serum β-HCG ^a	X																
Pneumococcal, Hib, Tetanus titers	X																
ALT/AST/total bilirubin	X	X		X		X		X		X				X		X	
Urine pregnancy test ^a		X		X		X		X		X				X		X	
ANC ^b	X	X	X	X	X	X	X	X	X	X	X	X	X				
CMV surveillance	X			X		X		X		X		X		X	X ^c		
Immune Monitoring	X			X				X						X		X	
Assess adverse events and SAEs ^d		X		X		X		X		X				X		X	
Record concomitant medications ^e		X		X		X		X		X				X		X	
Idelalisib dispensing/accounting		X		X		X		X		X				X		X	
Investigator response assessment ^f	X			X		X		X		X				X		X	

Abbreviations: β-HCG=beta human chorionic gonadotropin, ALT=alanine aminotransferase, AST=aspartate aminotransferase, Hib = Haemophilus Influenzae Type B

a For women of child bearing potential; Serum β-HCG to be collected at screening, urine pregnancy test to be collected at visits from first dose of idelalisib to EOS

b Absolute neutrophil count (ANC) will be monitored at least every two weeks for the first 24 weeks of idelalisib treatment

c CMV surveillance must be conducted approximately every 4 weeks throughout the course of idelalisib treatment

d For an AE of Diarrhea/Colitis: 1) Obtain history of onset and duration of diarrhea, including description of number of stools and stool composition, travel history, dietary changes and a medication review to identify possible diarrheogenic agents and 2) Perform physical examination including assessment for fever, dizziness, abdominal pain/cramping, and weakness

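### After Grade 4 neutropenia, Protocol Section 7.3.4 ends the required weekly blood counts one grade earlier than Table 5-2 does

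*Protocol*

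**What the plan says.** Two places in the protocol tell the site what to do about Grade 4 neutropenia.

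- **Section 7.3.4** states that "idelalisib must be interrupted and blood counts monitored at least weekly until ANC is" at or above 0.5 Gi/L. Of that same value it then says: "at which point, idelalisib may be resumed at a lower dose level". One threshold does two jobs: it ends the weekly counts and it opens the restart. The sentence before it covers a lesser event: "For subjects who develop Grade 3 neutropenia, blood counts must be monitored at least weekly". That sentence gives no stopping point.
- **Table 5-2 (Section 5.2.10), Grade 4 row** uses two thresholds. Under required actions, idelalisib is withheld and the site is told: "Monitor blood counts at least weekly until ANC" ≤ Grade 2. Under recommended actions it says: "May resume idelalisib at lower dose level when ANC grade is" ≤ Grade 3. The row above it, labelled Grade ≤ 3, carries the same weekly requirement to Grade 2 or better, with dosing maintained.

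The routine schedule is in Section 6.2.2: "Blood samples for ANC will be collected at Screening and every 2 weeks through Week 24". Table 6-1, footnote b, gives the same frequency: "Absolute neutrophil count (ANC) will be monitored at least every two weeks for the first 24 weeks of idelalisib treatment". The ANC row of that table has no entry under the every-4-week or every-12-week columns.

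On which text leads, Section 1.4 says "The management of these toxicities is described in" Table 5-2. Section 7.5.2 points to the table for dose modifications and to the investigator's brochure for toxicity management. Neither addresses how often counts are taken if the two texts differ.

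**The concern.** Both instructions are mandatory in form: 7.3.4 says must, and the table says required. They part at the point where a subject has just come up from Grade 4, may be back on drug at 100 mg BID, and is still at Grade 3. Section 7.3.4 itself reports treatment-emergent Grade 3 or 4 neutropenia, including febrile neutropenia, on idelalisib. A relapse after restart is what weekly counts would be there to catch.

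Two things follow. A site working from the 7.3.4 Grade 4 sentence could return such a subject to the routine ANC schedule too early. There is also a compliance ambiguity. Section 6 requires deviations from protocol procedures to be documented, yet stopping weekly counts at 0.5 Gi/L complies with one section and breaches a required action in another.

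This concerns subject safety and site conduct. It bears on no estimate, endpoint or listing.

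**Working it through.** The plan gives no figure to reproduce, so the check is a comparison of texts followed by a simple count.

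**Step 1. The rules side by side, for a subject who has had Grade 4 neutropenia**

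| Decision | Section 7.3.4, Grade 4 sentence | Table 5-2, Grade 4 row |
|---|---|---|
| Restart at lower dose | ANC ≥ 0.5 Gi/L | ≤ Grade 3 (recommended action) |
| End of weekly counts | ANC ≥ 0.5 Gi/L | ≤ Grade 2 (required action) |

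**Step 2. Does the conflict depend on the grade cut-offs?** The documents cite CTCAE 4.03 but do not print the neutrophil cut-offs. Matching the two restart rules implies that 0.5 Gi/L is the boundary between Grades 4 and 3, and that is assumed here. The restart points then agree, and the end points for weekly counts differ by one full grade. The existence of a conflict does not need the assumption. Section 7.3.4 uses one value for both decisions and the table uses two different grades, so no single ANC value can match both cells of the table.

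**Step 3. What the difference amounts to.** Let *k* be the number of weeks a restarted subject remains at Grade 3. The documents give no value for *k*, so 2, 4 and 8 weeks are assumed for illustration. The minimum number of counts over that time is:

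- Table 5-2, weekly: *k*
- Routine schedule up to Week 24, every 2 weeks: *k*/2
- Routine schedule after Week 24: 0 scheduled

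| *k* (weeks, assumed) | Table 5-2 | Routine, to Week 24 | Routine, after Week 24 |
|---|---|---|---|
| 2 | 2 | 2/2 = 1 | 0 |
| 4 | 4 | 4/2 = 2 | 0 |
| 8 | 8 | 8/2 = 4 | 0 |

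The post-Week 24 column is relevant because Section 3.4 sets no fixed end to treatment. The weekly rules are minimums, and the two right-hand columns apply only if every other Grade 3 instruction is set aside. The differences shown are therefore the largest possible, not the expected ones.

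**The case against.** The strongest reply is that a subject who recovers from Grade 4 to Grade 3 is already covered elsewhere. The table's Grade 4 row covers that subject, and so does the row above it. The 7.3.4 sentence on Grade 3 can be read to do so as well. A site would have to overlook all of these to go wrong. The two instructions can also both be obeyed, since counting weekly to Grade 2 satisfies 7.3.4 too. Section 1.4 places toxicity management in Table 5-2, and Section 5.2.10 treats only the recommended actions as guidelines and sends uncertain cases to the medical monitor. The direction of the protocol is therefore toward the table. The durations in the count are assumed, the lack of ANC after Week 24 is a feature of the routine schedule, and the SAP reports only 3 subjects enrolled.

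Most of this stands and is why the point is small. It does not remove the conflict. The Grade 3 sentence speaks of subjects who develop Grade 3 and has no stopping point. The sentence after it deals specifically with Grade 4 subjects and gives an explicit one, so a careful reader can take the specific rule as controlling. Pointing toward the table is not the same as saying that it overrides Section 7.3.4.

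Two objections to the remedy are also fair. The table's Grade 4 row includes neutropenic fever or infection, which the 7.3.4 sentence does not mention. Section 5.2.10 also expects exceptions for subjects who start with low counts, for whom Grade 2 may be out of reach. The rewording should not cut across either.

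**Conclusion.** The inconsistency is real and stands in the current text. After Grade 4 neutropenia, Section 7.3.4 allows weekly counts to end at the restart point, while Table 5-2 requires them until Grade 2 or better. The table is the rule to keep: it is stricter, it is labelled as required, and Section 1.4 names it as the place where toxicity management is described.

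The size is low. The discrepancy matters only at a site that applies the 7.3.4 Grade 4 sentence alone, and only while a restarted subject remains at Grade 3. The documents do not say whether any of the 3 enrolled subjects had Grade 4 neutropenia. That the gap is exactly one grade rests on reading 0.5 Gi/L as the Grade 4/Grade 3 boundary. The counts rest on the assumed durations.

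**What to change.** Leave Table 5-2 unchanged and amend the Grade 4 sentence of Section 7.3.4 so that the two decisions have separate thresholds. Keep its opening, "idelalisib must be interrupted and blood counts monitored at least weekly until ANC is", and continue: *≤ Grade 2, including after any restart; restart at the lower dose is allowed once ANC is ≤ Grade 3 (≥ 0.5 Gi/L)*. It would help to add a reference to the Table 5-2 neutropenia rows and Section 5.2.10. The wider trigger (neutropenic fever or infection) and the allowance for low starting counts would then carry over without being restated.

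The cost is one sentence of wording and no new procedure, because Table 5-2 already requires the counts. Under Section 9.2.1 the change needs documented ethics committee approval before it is implemented, so it is best included in the next amendment.

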7.3.5. Pulmonary Events

Documented bacterial, fungal, viral, and pneumocystis pneumonias have been observed in patients receiving idelalisib, primarily in patients with CLL. Some study subjects receiving idelalisib alone or in combination have developed evidence of pneumonitis without documented pulmonary infection.

Given the potential for infectious or drug-related pulmonary adverse events, clinicians should be particularly observant for evidence of respiratory events in subjects participating in this trial. Subjects who describe pulmonary symptoms (eg, dyspnea on exertion, cough, shortness of breath); manifest a decline from baseline of $\geq 5\%$ in oxygen saturation, or demonstrate evidence of pulmonary inflammation (eg, focal or diffuse interstitial pattern or ground-glass opacities on chest CT) should be evaluated. Potential bacterial, fungal, or viral etiologies should be assessed. Noninfectious etiologies such as pulmonary edema or thromboembolism should also be considered.

As appropriate for the clinical situation and culture results, subjects should be treated empirically or given specific antibiotics, antifungals, or antiviral agents for a cultured organism. Supportive care, including oxygen or mechanical ventilation, should be provided as necessary.

For subjects with suspected pneumonitis (eg, onset of cough, dyspnea, hypoxia and/or a diffuse interstitial pattern or ground-glass opacities on chest imaging without obvious infectious etiology), idelalisib should be interrupted (or discontinued if pneumonitis is Grade ≥ 2). Supportive care, including oxygen or mechanical ventilation, should be considered and provided as necessary. Consider bronchoscopy to evaluate for PJP, CMV and other organisms (bacterial and viral). Consider treatment with systemic corticosteroids. Consider empiric treatment of pneumocystis if bronchoscopy is contraindicated. Upon resolution, may resume idelalisib at lower dose level at investigator discretion and Gilead medical monitor agreement.

7.3.6. Secondary Malignancies

Subjects receiving idelalisib for CLL or iNHL have developed pre-malignant and secondary malignant diseases, such as basal cell carcinoma, myelodysplastic syndrome, myeloproliferative disorders, and more aggressive lymphoid malignancies (eg, have had Richter transformation). Generally this has occurred in subjects who have received multiple previous lines of therapy and when idelalisib is combined with other therapies such as rituximab or bendamustine. The specific association of the therapeutic agents with these types of events has not been determined.

There are reports of pre-malignant and malignant diseases that have developed in subjects who have been treated with bendamustine, including myelodysplastic syndrome, myeloproliferative disorders, acute myeloid leukemia, and bronchial carcinoma. The specific association of the therapeutic agents with these types of events has not been determined.

7.3.7. Tumor Lysis Syndrome

Tumor lysis syndrome has not been observed with idelalisib monotherapy.

When idelalisib is combined with other agents known to induce tumor lysis syndrome, prophylaxis with agents such as allopurinol may be considered. The benefit versus risk of prophylactic agents must be carefully considered given a potential of increased risk of severe skin toxicity.

Subjects with tumor lysis syndrome should receive rapid reversal of hyperkalemia, intravenous hydration, antihyperuricemic agents, and appropriate cardiac and renal support, including dialysis as indicated. Upon recovery to baseline functioning, such subjects should continue study treatment including study drug (idelalisib/placebo).

7.4. Investigator Requirements and Instructions for Reporting Adverse Events and Serious Adverse Events to Gilead

All SAEs, regardless of cause or relationship, that occur after the subject first consents to participate in the study (ie, signing the informed consent) and throughout the duration of the study, including the protocol-required post treatment follow-up period, must be reported to the eCRF database and Gilead Drug Safety and Public Health (DSPH) or designee as instructed. This also includes any SAEs resulting from protocol-associated procedures performed from screening onwards.

All AEs, regardless of cause or relationship, that occur from initiation of study medication until 30 days after last administration of idelalisib must be reported to the eCRF database as instructed.

Any SAEs and deaths that occur after the post treatment follow-up visit but within 30 days of the last dose of idelalisib, regardless of causality, should also be reported.

All AEs should be followed up until resolution if possible. If by the last day on study (including the off-study medication follow-up period) the AE has not resolved, then the AE will be followed up until the investigator and/or Gilead Sciences determine that the subject's condition is stable. However, Gilead Sciences may request that certain AEs be followed until resolution.

Investigators are not obligated to actively seek SAEs after the 30 day period. However, if the investigator learns of any SAEs that occur after study participation has concluded and the event is deemed relevant to the use of idelalisib, he/she should promptly document and report the event to Gilead DSPH or designee as instructed.

All AEs and SAEs will be recorded in the eCRF database within the timelines outlined in the eCRF completion guidelines.

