Study Design:	This study is an open-label, rollover study to provide idelalisib to subjects receiving GS-9820 in Study GS-US-315-0102 at the time of study closure.
Number of Subjects Planned:	Approximately 6 subjects
Target Population:	Subjects receiving GS-9820 in Study GS-US-315-0102 at the time of study closure who have objective evidence of clinical benefit defined as at least stable disease on imaging assessed by the IRC at final response assessment prior to enrollment in this study.

Duration of Treatment: Subjects will be treated until withdrawal from study drug, progressive disease, intolerable study drug-related toxicity, pregnancy, substantial noncompliance with study procedures, or study discontinuation. Idelalisib administration should only be continued in subjects with a positive benefit-risk profile assessment as per the investigator.

Diagnosis and Main Eligibility Criteria:

Inclusion Criteria

Subjects must meet all of the following inclusion criteria to be eligible for participation in this study:

- 1) Receiving GS-9820 in Study GS-US-315-0102 with objective evidence of clinical benefit defined as at least stable disease on imaging assessed by the IRC at the time of Study GS-US-315-0102 closure
- 2) For female subjects of childbearing potential, willingness to use a protocol recommended method of contraception during heterosexual intercourse from the signing of informed consent throughout the study treatment period and up to 30 days from the last dose of idelalisib (see [Appendix 2](#))
- 3) For male subjects of reproductive potential having intercourse with females of childbearing potential, willing to use a protocol recommended method of contraception during heterosexual intercourse and to refrain from sperm donation throughout the study treatment period and for 90 days following discontinuation of idelalisib (see [Appendix 2](#))
- 4) Willingness to comply with scheduled visits, drug administration plan, imaging studies, laboratory tests, other study procedures, and study restrictions, including mandatory prophylaxis for Pneumocystis jirovecii pneumonia (PJP). ***Note: Psychological, social, familial, or geographical factors that might preclude adequate study participation should be considered.***

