5. INVESTIGATIONAL MEDICINAL PRODUCTS

5.1. Randomization, Blinding and Treatment Codes

The study is open-label and non-randomized.

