5.2.9. Dose Levels

Idelalisib dose levels are shown in [Table 5-1](#). The starting dose level will be 150 mg BID. The lower dose level (Dose Level -1) is provided in case a subject requires a dose modification.

Table 5-1. Idelalisib Dose Levels

Dose Level	Dosing Regimen
Starting	150 mg BID
-1	100 mg BID

Abbreviation: BID=twice per day

Consistent with [Table 5-2](#), if a subject experiences an AE that is suspected to be related to idelalisib during the course of study, idelalisib administration may be held, as necessary, until the AE resolves or stabilizes to an acceptable degree (as defined in [Table 5-2](#)). Thereafter, idelalisib may be reinitiated at either the Starting Dose Level or at Dose Level -1 consistent with the instructions in Section [5.2.10](#). A further attempt at reinitiation of therapy at Dose Level -1 may be attempted if the investigator feels that a second rechallenge at that dose level is medically appropriate. If the subject cannot tolerate idelalisib after 2 rechallenges at Dose Level -1 for the same AE, then the subject should be discontinued from idelalisib treatment.

After an idelalisib dose reduction, the dose need not be re-escalated, even if there is minimal or no toxicity with the reduced dose. However, if the subject tolerates Dose Level -1 of idelalisib for \geq 4 weeks, then the dose may be increased back to Starting Dose Level, at the discretion of the investigator. Such a re-escalation may be particularly warranted if further evaluation reveals that the AE that led to the dose reduction was not related to idelalisib.

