Grade 3 (ALT/AST $> 5\text{-}20\times$ ULN) (Bilirubin $> 3\text{-}10\times$ ULN)	
Recommended Action: Withhold idelalisib.
 
Required Action:
 
• Monitor ALT, AST, ALP, and bilirubin at least 1x per week until all abnormalities are Grade ≤ 1.• If bilirubin abnormality is Grade < 3, resume idelalisib at same dose level. If bilirubin abnormality is Grade ≥ 3, resume at lower dose level.
Grade 4 (ALT/AST $> 20\times$ ULN) (Bilirubin $> 10\times$ ULN)	
Required Action:
 
• Withhold idelalisib.• Monitor ALT, AST, ALP, and bilirubin at least 1x per week until all abnormalities are Grade ≤ 1.• If bilirubin abnormality is Grade 4, discontinue idelalisib. 
Recommended Action: If bilirubin abnormality is Grade < 4, resume study drug at lower dose level.

Pneumonitis (dyspnea, cough, hypoxia without obvious infectious cause)	
Grade ≤ 1	Recommended Action: Withhold idelalisib until resolution to baseline. May resume at lower dose level or discontinue idelalisib at investigator discretion.
Grade ≥ 2	
Required Action:
 
• Discontinue idelalisib. 
Recommended Action:
 
• Consider bronchoscopy to evaluate for PJP, CMV and other organisms (bacterial and viral)• Consider treatment with systemic corticosteroids.• Consider empiric treatment of pneumocystis if bronchoscopy is contraindicated• Upon resolution, may resume idelalisib at lower dose level at investigator discretion and /Gilead medical monitor agreement

NCI CTCAE Grade ^a	Idelalisib
Pneumocystis jirovecii pneumonia (PJP)	
Any Grade	Required Action: Discontinue idelalisib
Uequivocal CMV infection^c	
Any Grade	Required Action: 
Interrupt idelalisib upon unequivocal clinical or laboratory evidence of CMV infection.Treat according to established clinical guidelines.If the benefits of resuming idelalisib are judged to outweigh the risks, consideration should be given to administering pre-emptive CMV therapy.
Other Nonhematological Adverse Events	
Grade ≤ 2	Recommended Action: Maintain current dose level and schedule
Grade ≥ 3	Recommended Action: Withhold idelalisib until Grade ≤ 1 . May resume idelalisib at initial or lower dose level or discontinue idelalisib at investigator discretion.

a CTCAE, Version 4.03.

b See section [6.2](#) and [7.3.2](#) for additional requirements regarding an AE of diarrhea

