5.5. Discontinuation from Study

Subject study participation may be ended due to any of the follow reasons:

- Withdrawal of consent
- Objective evidence of disease progression.
- Unacceptable toxicity or unable to tolerate a second rechallenge for the same AE.
- Any subject who becomes pregnant or begins breastfeeding.
- Initiation of non-protocol specified anticancer therapy.
- Noncompliance with idelalisib administration, study procedures, or study requirements.
- The investigator may discontinue idelalisib, if it is not in the subject's best interest to continue.
- Any subject who is lost to follow-up.
- Death
- Discontinuation of study by the Sponsor, a regulatory agency, or an EC
- Any subject who is diagnosed with any grade SJS or TEN, Grade ≥ 2 pneumonitis, or any grade PJP.
- Any subject whose benefit-risk profile is not deemed positive by the investigator should discontinue study drug.

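### Section 7.3.7 and Table 5-2 give different recovery thresholds, and a different choice about stopping, for restarting idelalisib after tumor lysis syndrome

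*Protocol*

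**What the plan says.** Protocol Section 7.3.7 opens with "Tumor lysis syndrome has not been observed with idelalisib monotherapy". It goes on to supportive care (treatment of hyperkalemia, hydration, cardiac and renal support, dialysis where indicated) and ends with the restart instruction: "Upon recovery to baseline functioning, such subjects should continue study treatment including study drug (idelalisib/placebo".

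Sections 1.4 and 7.5.2 both point to Table 5-2 for the management of toxicities. That table has no tumor lysis row. Its closest entry is the Other Nonhematological Adverse Events row. At Grade 3 or higher this recommends withholding until the event is Grade 1 or lower, and then: "May resume idelalisib at initial or lower dose level or discontinue idelalisib at investigator discretion". Section 5.2.10 explains the standing of such entries: "When a modification is indicated as a recommendation, it serves as a guideline". For events suspected to be related to idelalisib, Section 5.2.9 adds that after a hold "idelalisib may be reinitiated at either the Starting Dose Level or at Dose Level -1 consistent with the instructions in Section" 5.2.10.

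A general condition sits above all dosing. The synopsis states: "Idelalisib administration should only be continued in subjects with a positive benefit-risk profile assessment as per the investigator". Section 5.5 repeats it: "Any subject whose benefit-risk profile is not deemed positive by the investigator should discontinue study drug".

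**The concern.** Section 7.3.7 reads as a complete instruction with one condition, recovery. It does not refer to Table 5-2, to the benefit-risk condition or to Section 5.5. A site that opens the protocol at the tumor lysis section finds a direction to carry on. A site that opens it at the dose-modification table finds a graded threshold and a discretionary choice that includes stopping.

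The matter at stake is re-exposure after an event that can be life-threatening. That is a patient-management question first. It also shows in what the SAP reports for each subject: the study drug administration listing (SAP Section 4.2), the listing of reasons for premature discontinuation (SAP Section 4.1), and the treatment-emergent window, which runs to 30 days after permanent discontinuation (SAP Section 7.1.5.1).

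**Working it through.** No arithmetic applies. There is no hypothesis, sample-size calculation or stated figure to reproduce, so the check sets the passages side by side.

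**Step 1: which Table 5-2 row applies.** Tumor lysis syndrome is not named, so the catch-all nonhematological row is the only candidate. The instruction then depends on grade. Section 7.2.2 grades by CTCAE 4.03 and uses the wording of Table 7-1 only where CTCAE has no criterion. CTCAE is not among the documents, so the grade has to be assumed. The cardiac and renal support described in 7.3.7 make Grade 3 or higher plausible.

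**Step 2: the comparison.**

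| Element | Section 7.3.7 | Table 5-2, catch-all row, Grade 3 or higher | Result |
|---|---|---|---|
| Interruption | Not stated; implied by the reference to recovery | Withhold (recommended) | Silence, can be filled from the table |
| Recovery threshold | Baseline functioning, undefined | Grade 1 or lower | Different |
| After recovery | Should continue | May resume or discontinue, investigator's discretion | Different |
| Dose level | Not stated | Initial or lower | Silence, can be filled from the table and 5.2.9 |

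**Step 3: whether the thresholds really diverge.** They can, in both directions. Take a subject whose relevant organ function was already abnormal at Grade 2 before the event. Return to that state could meet 7.3.7 without meeting the table. A subject with no prior abnormality whose event has improved to Grade 1 meets the table but may not be back to baseline. These are illustrations, not cases in the documents. Table 5-2 itself keeps the two ideas apart: low-grade pneumonitis is held until return to baseline, whereas the catch-all row uses a grade.

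**Step 4: sensitivity to the grade assumption.** At Grade 2 or lower the catch-all row recommends keeping dose and schedule. The difference over discontinuation then disappears. What remains is a mismatch between carrying on unchanged and carrying on once recovered. The main point therefore rests on Grade 3 or higher.

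**Step 5: comparison within Section 7.3.** The neutropenia text (7.3.4, Grade 4) and the pneumonitis text (7.3.5) state an interruption, use permissive wording for resumption and refer to the dose level. Section 7.3.7 does none of these. Its mention of placebo does not fit a protocol in which "The study is open-label and non-randomized", and Section 7.3.2 refers to resuming rituximab although Section 5.3.1 bars other anticancer therapy except corticosteroids. This suggests wording carried over from another protocol; the documents do not say so.

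**The case against.** The strongest reply is that the passages can be followed together. Both are soft: 7.3.7 says should, and the table entry is a recommendation that the investigator may vary. Continuing is one of the choices that the table allows. A site that holds the drug until the event is both at baseline and at Grade 1 or lower, and then resumes at either level, satisfies both passages. Section 5.5 also lets the investigator stop idelalisib when continuing is not in the subject's best interest, so stopping is available somewhere in the protocol whatever 7.3.7 says.

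Much of this stands, and it rules out several stronger readings.

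- A reader might infer that the passages clash on every element of the restart. They do not. On interruption and dose, 7.3.7 is silent, and Table 5-2 and Section 5.2.9 can fill the gap.
- A reader might infer that 7.3.7 overrides the benefit-risk condition. The more natural reading is that the synopsis and Section 5.5 set a general condition on every instruction to resume, which need not be repeated in each toxicity section. The fair criticism is only that 7.3.7 does not refer to it.
- A reader might infer that the inconsistency makes the SAP listings unreliable. Table 5-2 alone already permits initial dose, lower dose or discontinuation, so subjects could differ in these respects even if 7.3.7 matched it. The listings would still record what happened.

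The reply does not remove two things. The thresholds are different tests, and an investigator who stops the drug in a recovered subject uses an option that the table offers while departing from what 7.3.7 says should happen. Sections 1.4 and 7.5.2 direct sites to Table 5-2 but do not say that it prevails over 7.3.7.

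**Conclusion.** The point holds as a narrow internal inconsistency of low severity. Section 7.3.7 and the Table 5-2 catch-all row differ on the recovery threshold and on whether discontinuation is among the choices, and 7.3.7 does not refer to the general benefit-risk condition.

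This rests on one assumption, that the event would be Grade 3 or higher. It takes no view on which clinical rule is right.

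The practical size is small. The protocol reports no tumor lysis with monotherapy, Section 5.3.1 excludes the combination setting that 7.3.7 discusses, and SAP Section 1.3 records 3 subjects enrolled. A reader might be tempted to express the impact as a share of those subjects, but that would only restate the sample size; the documents give no sign that any subject was affected. The SAP tests no hypothesis (Section 1.3), plans no efficacy analysis (Section 6) and reports adverse events as listings (Section 7.1.6), so no summary estimate is affected. The reason to act is that the inconsistency concerns re-exposure after a potentially life-threatening event and costs almost nothing to remove.

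**What to change.** Reconcile Section 7.3.7 with Table 5-2 so that a site finds one restart rule wherever it looks. That rule should have one recovery threshold, with baseline functioning defined if the term is kept, and should say plainly whether discontinuation is an option and who decides. This could be a cross-reference from 7.3.7 to the applicable row of Table 5-2, or a tumor lysis row in the table that matches 7.3.7. In either case 7.3.7 should refer to the benefit-risk condition in the synopsis and Section 5.5. The reference to placebo can be removed in the same edit. The sponsor's clinicians must settle the content of the rule.

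The cost is a wording change in one section and, if chosen, one table row. It needs no new data, visits, procedures or analyses.
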